on the region that best represents their pain and writing the number (a whole number) on the form; scores range from 0 (no pain) to 100 (severe intolerable pain). The Opioid Use questionnaire will be used to document average opioid use following discharge. Both questionnaires will be completed by all participants at POD1, week 2 and week 6 visits. The VAS will be given to the participant with the intake form that is provided by the orthopedic technician, and the investigator will provide the Opioid Use questionnaire to the participant during the visit, and review the MAR Summary to obtain and calculate the total MME from POD0 to POD1 using MDCalc . Prior to ending the visit, the investigator will ask participants to bring in their opioids to be physically counted at their week 2 and week 6 visits.

Step 6: The investigator will provide a reminder phone call 1-2 days prior to the week 2 and week 6 appointments to ensure participants remember to bring in their medication.

Step 7: Participants return for the week 2 and week 6 visits. They are given VAS and Opioid Use questionnaires to complete, and opioid medication is counted. Once opioids have been accounted for, MME will be calculated.

10.2 Data Collection:

Describe all the data variables, information to be collected, the source of the data, and how the data will be operationally measured.

Injection type: Dichotomous variable. Trigger point or sham injection.

Visual analogue scale: Discrete variable. Will be scaled from 0 (no pain) to 100 (severe intolerable pain) and will be measured at POD1, week 2, and week 6. The VAS will be presented to the participant on paper.

Morphine milligram equivalent (MME): Discrete variable. Will be measured from POD 0 to POD1, then a total MME will be calculated from POD1 to week 2 and week 2 to week 6. This will be calculated utilizing the MME calculator on MDCalc.

Block: Categorical variable. Spinal, adductor or femoral nerve block determined by anesthesiology.

Age: Continuous variable. Age stated in years at time of surgery as stated in EHR.

Prior Pain Medications: Categorical variable. Obtained from EHR.

Discharge disposition: Dichotomous variable. Discharge to skilled nursing facility or home, discharge disposition will be reviewed in the discharge summary.

Active Duty, Dependent, Retiree: Categorical Variable.

Sex: Categorical (male, female). Obtained from EHR.

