11.0 Statistical/Data Analysis Plan

11.1 Data Analysis Plan and Statistical Considerations:

List the statistical methods to be used to address the primary and secondary objectives, specific aims, and/or research hypotheses. Explain how missing data and outliers will be handled in the analysis. The analysis plan should be consistent with the study objectives. Include any subgroup analyses (e.g., gender or age group). Specify statistical methods and variables for each analysis. Describe how confounding variables will be controlled in the data analysis.

Demographic (age at time of surgery, BMI, sex, active duty/dependent/retiree status), medical (ICD code, nicotine use, history of diabetes, prior pain medications), laterality of the TKA (left or right), discharge disposition, and anesthetic block type (spinal, adductor, or femoral nerve block) data will be summarized overall and as a function of injection group using descriptive statistics (eg, mean, standard deviation, median, minimum, maximum, frequency, percentages) and 95% confidence intervals to describe the sample. Appropriate inferential statistics (eg, independent samples t tests, chi square tests) will be performed to determine if there are statistically significant differences in any of these variables between the two injection groups. If so, multivariable techniques (eg, ANOVA or regression) including these potentially confounding variables in the analyses and/or stratification will be undertaken.

VAS pain scores and the dosage (MME) of opioids will be evaluated in patients as a function of injection type (ie, trigger point injection vs. sham injection) at each time point. Data will be assessed for normality and homogeneity of variance to determine whether parametric (eg, independent samples t tests, repeated measures ANOVAs) or nonparametric (eg, Wilcoxon Mann Whitney tests, Skillings-Mack tests) methods are appropriate.

In addition, the number of patients with a VAS>40 (indicating a “significant” level of pain) will be calculated and compared in each group and at each time point using the chi-square test (or the Fisher’s Exact test if assumption regarding minimum expected cell counts is not met) as well as McNemar’s tests.

The critical alpha level will be set at .05. Missing data will be handled using the “pairwise deletion” method; this method still includes patients with some missing data in the analyses when possible.

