11.5 Please provide a justification for your sample size

We used G*Power 3.1 (Dusseldorf Germany) to perform sample size calculations for our study. We designed these calculations using the primary outcome measure (ie, VAS pain scale rating in each injection group) which will be statistically compared using the independent samples t test or its nonparametric equivalent (ie, the Wilcoxon Mann Whitney test) if the assumptions for the independent samples t test (ie, normality and homogeneity of variance) are not met.

Using the more conservative Wilcoxon Mann Whitney test (Type 1 error/alpha level=.05 (two tailed) and power=.80), a sample size of 30 (ie, 15 in the trigger point group and 15 in the sham group) would allow us to detect a statistically significant difference in VAS pain scale ratings if a “large” effect size of 1.1 was obtained. A “large” effect size of 1.1 corresponds to an average difference (delta) in VAS scores between groups of ≥ 28 units and an average standard deviation in each group of ≤ 25 units. This standard deviation is similar to Mayoral et al. (2013) who reported an average standard deviation of 25 units for the VAS at the 1 month follow up. Note that Mayoral et al. (2013) did not report VAS scores on POD1, although their average difference (delta) in VAS scores at 1 month was smaller than 28 units.

If up to 5 patients (eg, 30%) per group drop out of the study, a lower sample size of 20 (ie, 10 in the trigger point group and 10 in the sham group) would allow us to detect a statistically significant difference in VAS pain scale ratings if a larger effect size of 1.4 was obtained. This “larger” 1.4 effect size corresponds to an average difference (delta) in VAS scores between groups of ≥ 35 units and an average standard deviation in each group was ≤ 25 units (again using the more conservative Wilcoxon Mann Whitney test (Type 1 error/alpha level=.05 (two tailed) and power=.80)).

In summary, our aim of including at least 10-15 patients per group would allow us to statistically detect a “large” effect of trigger point injections (relative to sham injections) on VAS pain ratings assuming our standard deviations were \leq to the standard deviations in VAS pain scales reported by Mayoral et al. (2013). In addition, if statistically significant differences are not found, the data from our

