Patients will be recruited through use of a HIPAA Waiver to access joint surgeon case lists. Patients scheduled for a TKA will be contacted by the principal investigator and informed of the study. Those who desire to participate will have study inclusion/exclusion criteria reviewed to determine eligibility. Those eligible will be scheduled a consent appointment. The investigator will offer to email (or provide by hard copy) consent document to review prior to the appointment. When patients return for consenting, they will be taken to a private room (clinic exam room or private room in the PACU) to conduct the consent procedures. Consent documents will be reviewed with patients and any questions asked will be answered. Patients who desire to enroll in the study will sign the consent documents. The investigator will sign the consent documents, then provide a copy to the patient. During the recruitment and consenting phase, the PI or AI will not be in military uniform or have their rank visible.

13.5 DoDI 3216.02 requires an ombudsman to be present during recruitment briefings when research involves greater than minimal risk and recruitment of Service members occurs in a group setting. If applicable, you may nominate an individual to serve as the ombudsman.

N/A
 Propose ombudsman

13.6 Withdrawal from Study Participation:

Explain the process for withdrawal and specify whether or not the subjects will be given the opportunity to withdraw their data or specimens in the event they wish to withdraw from the study

At any point in the study participants can self-withdrawal from the study if they have a poor response to the injections, are unable to tolerate all injections, not willing to complete questionnaires, intraoperative complications (pulmonary embolism, deep vein thrombosis, surgical site infection, multiple or other), not willing to bring in their medications or if they choose to no longer participate in the study. However, any data collected prior to withdrawal will still be analyzed.

14.0

Risks and Benefits

14.1

Risks of Harm:

Identify all research-related risks of harm to which the subject will be exposed for each research procedure or intervention as a result of participation in this study. Consider the risks of breach of confidentiality, psychological, legal, social, and economic risks as well as physical risks. Do not describe risks from standard care procedures; only describe risks from procedures done for research purposes

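### Pairwise deletion with withdrawal allowed for poor response can bias the week 2 and week 6 VAS comparisons, in either direction, if such withdrawal differs between arms

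*Combined protocol and SAP*

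**What the plan says.** Section 11.1 compares VAS and MME by injection group at each time point and gives one missing-data rule, pairwise deletion, adding that "this method still includes patients with some missing data in the analyses when possible". It states no imputation, no model for incomplete follow-up, no sensitivity analysis and no comparison of withdrawals by arm.

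Section 10.2 says that VAS "will be measured at POD1, week 2, and week 6". Section 11.5 says that the primary outcome will be "statistically compared using the independent samples t test or its nonparametric equivalent", the Wilcoxon Mann Whitney test.

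Section 13.6 lets participants leave "if they have a poor response to the injections, are unable to tolerate all injections", or for complications, unwillingness to complete questionnaires or bring in medications, or by choice. It adds that "any data collected prior to withdrawal will still be analyzed". It describes no data collection after withdrawal.

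Section 11.5 considers dropout in these terms: "If up to 5 patients (eg, 30%) per group drop out of the study". Its only response is to raise the detectable effect size from 1.1 to 1.4.

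**The concern.** In a pain trial, a poor response to the injections is closely related to the outcome being measured. A participant who leaves for that reason after POD1 is absent from every later group comparison. The POD1 score is kept, but a two-sample test at week 6 has no way to use it. The later comparisons then contrast those who stayed in one arm with those who stayed in the other.

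If the two arms lose different numbers or kinds of patients, the difference between those who stayed is not the difference between the groups as assigned. Unequal loss is plausible: section 10.1 gives one arm eight intramuscular injections and the other a needle placed in the epidermis with nothing injected. Section 11.5 treats dropout only as lost power, so nothing in the plan would detect or limit the bias. Scores not collected at weeks 2 and 6 cannot be recovered afterwards.

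**Working it through.** **Inputs from the documents.** 15 per group, SD 25, design difference 28, two-sided alpha 0.05, power 0.80, up to 5 leavers per group (all 11.5); maximum 50 per group (11.2).

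**Assumptions, because the documents give no figures.** No true effect; normal scores, ignoring the 0 to 100 limits; correlation r between the score that prompts leaving and the later VAS, mainly 0.5 to 0.7; number of leavers k by arm.

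**The plan's own figure.** Noncentral t power with the Wilcoxon efficiency 3/π gives 0.810 for 15 per group at d = 1.1, and 0.822 for 10 per group at d = 1.4. The stated sample sizes reproduce and are not in question.

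**Size of the bias.** Let the k highest POD1 scorers of n leave one arm. With S the expected sum of the k largest of n standard normal values, the mean of those who stay shifts at the later visit by

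bias = −r × SD × S / (n − k).

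For n = 15 and SD = 25:

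| k | S | S/(n − k) | r = 0.5 | r = 0.7 |
|---|---|---|---|---|
| 2 | 2.984 | 0.2295 | −2.9 | −4.0 |
| 3 | 3.932 | 0.3276 | −4.1 | −5.7 |
| 5 | 5.162 | 0.5162 | −6.5 | −9.0 |

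Simulation agrees: −2.7 and −4.0, −4.1 and −5.6, −6.5 and −9.2. The arm that loses its high scorers looks better by that amount.

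**By pattern of loss** (simulation, 15 per arm, r = 0.5 to 0.7, trigger point minus sham, t test):

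| Leavers, trigger point vs sham | Bias | Chance of a significant false benefit |
|---|---|---|
| 0 vs 0 | 0 | 0.025 |
| 3 vs 0 | −4.1 to −5.6 | 0.063 to 0.089 |
| 5 vs 0 | −6.5 to −9.2 | 0.092 to 0.149 |
| 5 vs 2 | −3.5 to −5.0 | 0.059 to 0.083 |
| 5 vs 5 | 0 | 0.029 to 0.036 |
| 0 vs 5 | +6.5 to +9.2 | 0.005 to 0.003 |

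The last row is the mirror image: a bias against the injections, which would hide a real benefit.

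**Larger samples.** At 50 per group with 15 vs 0 leaving, the bias is −6.0 to −8.6 and the chance of a false benefit is 0.201 to 0.370. The standard error shrinks but the bias does not.

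**What a likelihood model recovers** (15 per arm, 5 vs 0, POD1 and the later visit analyzed together):

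| Leaving depends on | r | Pairwise deletion | Likelihood model | Share left |
|---|---|---|---|---|
| recorded POD1 score | 0.5 | −6.5 | −0.1 | near 0 |
| recorded POD1 score | 0.7 | −9.0 | 0.0 | 0 |
| unrecorded later pain | 0.5 | −12.8 | −10.1 | 10.1/12.8 = 79% |
| unrecorded later pain | 0.7 | −12.9 | −7.3 | 7.3/12.9 = 57% |

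The model corrects leaving explained by recorded scores. When unrecorded later pain drives leaving, more than half of the bias stays. With everyone followed, simulated bias is about 0 and type I error about 0.05.

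**The case against.** A reader might infer that the plan will drop its worst responders from the trigger point arm and so show a false benefit. The documents do not support that, for four reasons.

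- **Withdrawal is voluntary and open to both arms.** Poor response is one of several reasons and is not defined by a VAS value. Others, such as unwillingness to complete questionnaires, need not relate to pain.
- **The direction is not fixed.** The one remark in the documents on which arm may have more pain is in section 14.1, and it names the sham arm. Section 10.1 also expects the anesthetic block to be active during the sham procedure and uses a drape in both arms, which weakens the argument for unequal tolerance without removing it.
- **Pain-related leaving is not enough by itself.** With no true effect and the same loss in both arms, the mean difference stays unbiased, although the t test's type I error rises slightly (0.057 to 0.073 for 5 vs 5).
- **Section 11.5 is conditional and speaks of each group.** It does not predict 5 leavers, still less 5 from one arm.

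The size also needs context. A bias of 3 to 6 units (2 or 3 leavers) is below the standard error of 25 × √(2/15) = 9.1 units and well below the 28-unit design difference.

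Section 11.1 also names repeated measures ANOVA and Skillings-Mack tests as possible methods. They are examples, and neither is specified as a way to handle outcome-related loss; standard repeated measures ANOVA needs complete cases.

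All of this limits the claim to a risk of unknown direction. It does not remove the risk, because the plan has no means of detecting or limiting unequal loss.

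**Conclusion.** The point holds as a risk to the week 2 and week 6 VAS comparisons, conditional on outcome-related withdrawal differing between arms. Under the stated assumptions, with 2 to 5 of the highest POD1 scorers leaving one arm only, the bias is about 3 to 9 units toward that arm. At the top of that range it is roughly a third of the design difference (9/28 = 32%). It is zero on average if loss is equal.

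POD1 is largely unaffected because scores recorded before withdrawal are kept; the exception is anyone who leaves on POD0 without giving a score. The numbers of leavers by arm and the correlations are assumptions. The change is worth making before data are analyzed, but the design does not depend on it.

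**What to change.** 1. In 11.1, replace pairwise deletion for VAS with a likelihood-based mixed model: arm, visit, arm by visit and a within-patient covariance, using every observed score and keeping patients in their assigned arm.
2. Add one sensitivity analysis that gives leavers worse assumed scores at the missed visits, since the model corrects fully only for leaving that depends on recorded scores.
3. Report withdrawals and their reasons by arm and visit.
4. Amend 13.6 so that participants who stop for poor response may agree to complete the week 2 and week 6 VAS. This is the only step that addresses leaving driven by unrecorded pain directly. It depends on the participant's agreement.

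The cost is slightly more analysis work, in R, which the references already cite, and a small wording change to 13.6 and possibly the consent form.

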11.5 Please provide a justification for your sample size

We used G*Power 3.1 (Dusseldorf Germany) to perform sample size calculations for our study. We designed these calculations using the primary outcome measure (ie, VAS pain scale rating in each injection group) which will be statistically compared using the independent samples t test or its nonparametric equivalent (ie, the Wilcoxon Mann Whitney test) if the assumptions for the independent samples t test (ie, normality and homogeneity of variance) are not met.

Using the more conservative Wilcoxon Mann Whitney test (Type 1 error/alpha level=.05 (two tailed) and power=.80), a sample size of 30 (ie, 15 in the trigger point group and 15 in the sham group) would allow us to detect a statistically significant difference in VAS pain scale ratings if a “large” effect size of 1.1 was obtained. A “large” effect size of 1.1 corresponds to an average difference (delta) in VAS scores between groups of ≥ 28 units and an average standard deviation in each group of ≤ 25 units. This standard deviation is similar to Mayoral et al. (2013) who reported an average standard deviation of 25 units for the VAS at the 1 month follow up. Note that Mayoral et al. (2013) did not report VAS scores on POD1, although their average difference (delta) in VAS scores at 1 month was smaller than 28 units.

If up to 5 patients (eg, 30%) per group drop out of the study, a lower sample size of 20 (ie, 10 in the trigger point group and 10 in the sham group) would allow us to detect a statistically significant difference in VAS pain scale ratings if a larger effect size of 1.4 was obtained. This “larger” 1.4 effect size corresponds to an average difference (delta) in VAS scores between groups of ≥ 35 units and an average standard deviation in each group was ≤ 25 units (again using the more conservative Wilcoxon Mann Whitney test (Type 1 error/alpha level=.05 (two tailed) and power=.80)).

In summary, our aim of including at least 10-15 patients per group would allow us to statistically detect a “large” effect of trigger point injections (relative to sham injections) on VAS pain ratings assuming our standard deviations were \leq to the standard deviations in VAS pain scales reported by Mayoral et al. (2013). In addition, if statistically significant differences are not found, the data from our

study can be used to perform sample size calculations to power future larger studies that could potentially detect smaller effects. Our data can also be used for potential future meta-analyses (ie, the statistical combination of the results of multiple studies addressing a similar research question).

Addendum:

Sample sizes for other combinations of the standard deviation and difference in means (Delta) are

shown in the table below for illustrative purposes only. The “effect sizes” for these combinations are derived using Cohen’s D (Cohen, 1988). A larger sample size is necessary to detect a smaller “true effect.”

Delta	SD	n	Cohen_D	Effect_Size
20	18.5	15	1.08	large
25	18.5	10	1.35	large

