The plan is to use 10-15 participants per group, although if time and resources permit, we will include more patients to increase the power of the study and

account for possible dropouts up to a maximum of 50 patients per group. Recruitment and enrollment will end once the target sample size has been achieved.

11.2 Sample Size:

The plan is to use 10-15 participants per group, although if time and resources permit, we will include more patients to increase the power of the study and account for possible dropouts up to a maximum of 50 patients per group (maximum of 100 patients total).

11.3 Total number of subjects requested (including records and specimens):

100

11.4 If you are recruiting by study arm, please identify the arms of the study and how many subjects will be enrolled in each arm

Experimental (ie, trigger point injection) group will include 10-15 patients (up to a maximum of 50 patients) and placebo (ie, sham injection) group will include 10-15 patients (up to a maximum of 50 patients). Recruitment and enrollment will end on 31 December 2025.

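### Section 11.5 derives 10 per group as completers, but 11.1, 11.2 and 11.4 use 10 as the lower bound of enrolment, where the stated .80 power does not survive the plan's own drop-out

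*Combined protocol and SAP*

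**What the plan says.** Section 11.5 bases its calculation on the VAS, the primary outcome: "Using the more conservative Wilcoxon Mann Whitney test (Type 1 error/alpha level=.05 (two tailed) and power=.80". It gives two scenarios.

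- **All complete.** The size is "a sample size of 30 (ie, 15 in the trigger point group and 15 in the sham group"), with 80% power "if a “large” effect size of 1.1 was obtained". This is translated into a difference in "VAS scores between groups of ≥ 28 units and an average standard deviation in each group of ≤ 25 units".
- **After drop-out.** "If up to 5 patients (eg, 30%) per group drop out of the study, a lower sample size of 20" (10 per group) is said to need a larger effect of 1.4, that is, at least 35 units with the same SD.

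The summary paragraph of 11.5 joins the two: "our aim of including at least 10-15 patients per group would allow us to statistically detect" a large effect. The only condition it repeats is the one on the SD.

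Sections 11.1 and 11.2 state the recruitment plan: "The plan is to use 10-15 participants per group". More patients, up to 50 per group, are to be included if time and resources permit, partly to allow for drop-outs. Section 11.4 answers the form's question about how many subjects will be enrolled in each arm with the same 10 to 15. It ends enrolment on 31 December 2025, while 11.1 ends it once the target size is reached.

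**The concern.** The number 10 has two meanings. In 11.5 it counts patients left from 15 after losses. In 11.4 it is the smallest number to be enrolled, with no allowance for losses. A trial that enrols 10 per group therefore complies with the plan, yet it does not start from the position that 11.5 analysed.

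The summary sentence adds to this by using one label for both ends of the range, although the text just above it separates a large effect (28 units) from a larger one (35 units). If the trial closes at the lower end and finds no difference, a reader could take it as having had 80% power for a difference of 28 to 35 units when it had clearly less. That matters because 11.5 itself notes that the 1-month difference in the cited dry needling trial was below 28 units.

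**Working it through.** **Inputs, all from 11.5:** two-sided alpha .05; target power .80; Wilcoxon Mann Whitney test; SD 25; effect sizes 1.1 (28/25 = 1.12, given as 1.1) and 1.4 (35/25); 15 or 10 per group; drop-out of up to 5 per group, given as 30% (5/15 = 33%). The enrolment minimum of 10 per group is from 11.1, 11.2 and 11.4.

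**Method.** The plan says "We used G*Power 3.1 (Dusseldorf Germany) to perform sample size calculations for our study". The matching approximation for normal data is the noncentral t with the group size multiplied by the efficiency of the Wilcoxon test, 3/π = 0.955:

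- m = n × 3/π; df = 2m − 2; noncentrality = d × √(m/2)
- power = P(|T| > t at 0.975 with df)

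Each setting was also simulated with the exact Mann-Whitney test on normal data (20,000 runs or more).

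**Step 1: reproduce the plan.**

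- n = 15, d = 1.1: m = 14.32, df = 26.65, noncentrality = 1.1 × √7.16 = 2.94, critical t = 2.05. Power 0.81 (simulated 0.80).
- n = 10, d = 1.4: m = 9.55, df = 17.10, noncentrality = 1.4 × √4.77 = 3.06, critical t = 2.11. Power 0.82 (simulated 0.80).

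Both stated figures are right. By the same approximation, 15 and 10 are the smallest group sizes that reach .80.

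**Step 2: apply the plan's drop-out to its minimum enrolment.** 15 enrolled less 5 leaves 10, as 11.5 says. 10 enrolled × (1 − 0.30) leaves 7. At the exact ratio 5/15 it is 6.7.

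**Step 3: power at 7 per group** (m = 6.68, df = 11.37, critical t = 2.19).

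| d | Difference at SD 25 | Noncentrality | Approximation | Exact test, simulated |
|---|---|---|---|---|
| 1.4 | 35 | 2.56 | 0.65 | about 0.60 |
| 1.1 | about 28 | 2.01 | 0.45 | about 0.40 |

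**Step 4: difference detectable with 80% power, SD 25.**

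- 15 per group (approximation): d = 1.09; 1.09 × 25 = 27 units
- 10 per group (approximation): d = 1.36; 1.36 × 25 = 34 units
- 7 per group (approximation): d = 1.68; 1.68 × 25 = 42 units
- 7 per group (exact test): d = 1.68 has simulated power of only 0.76; about 1.77 is needed, and 1.77 × 25 = 44 units

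The two methods differ noticeably at 7 per group, so any figure quoted there should name its method.

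**The case against.** A reader might infer that the plan claims 80% power for an effect of 1.1 with 10 per group, where the actual power is 0.62 by the approximation (simulated 0.60). The documents do not support that reading. The paragraph before the summary says that 10 per group needs 1.4 and at least 35 units, and the addendum table in 11.5 labels both 1.08 (n = 15) and 1.35 (n = 10) as large. On those labels the summary sentence is loose, not false. Nor is there an arithmetic error, since both calculations reproduce.

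It can also be said that the 7-per-group case is not in the plan. The 30% is an upper figure applied to 15, recruitment may go to 50 per group, and not everyone who drops out is lost to every analysis. Section 13.6 keeps data collected before withdrawal and 11.1 uses pairwise deletion, so a patient lost after POD1 still counts at POD1.

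These points limit the concern but do not remove it. The larger enrolment depends on time and resources and does not change the minimum. No other drop-out rate is given. The POD1 comparison could keep close to 10 per group, but the week 2 and week 6 comparisons could not if 30% were lost by then. The plan nowhere gives the power for 10 enrolled with losses.

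**Conclusion.** The point holds as a minor inconsistency in the stated power. The calculations in 11.5 are correct for 15 and 10 completers per group. They do not carry over to 10 enrolled per group, which 11.1, 11.2 and 11.4 allow. With 10 enrolled and 30% lost, about 7 per group remain at the later visits. Power is then about 0.60 (exact test) to 0.65 (approximation) for 35 units, and 0.40 to 0.45 for 28 units. The detectable difference rises from about 34 units at 10 completers to between 42 and 44.

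This assumes normal data, SD 25, equal groups, and the plan's 30% loss applied to the minimum enrolment. If 10 means completers throughout, the stated .80 at 1.4 stands, and only the summary sentence needs to be made more precise.

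**What to change.** 1. In 11.5, replace the summary sentence with two statements: 15 completers per group give 80% power for an effect size of 1.1 (about 28 units at SD 25); 10 completers per group give 80% power only for 1.4 (about 35 units).
2. In 11.1, 11.2 and 11.4, state that 10 is the number of completers expected from 15 enrolled per group.
3. If instead 10 may be the number enrolled, say so and restate the lower-bound power: with 30% lost, about 7 per group remain at the later visits, power is about 0.6 at 1.4, and the detectable difference is about 42 units (G*Power-type approximation) or 44 units (exact test). Name the method used for each figure. Add that patients lost after POD1 still contribute to the POD1 comparison.

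The cost is wording only. No procedure or analysis changes. Under option 3 the stated power at the lower bound becomes less favourable.
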